4.0 Patient Eligibility

Inclusion:

- 4.1 Previously untreated AML patients, except those who have received prior therapy with hydroxyurea, single agent chemotherapy (e.g. decitabine), hematopoietic growth factors, biological or targeted therapies are allowed.
- 4.2 Age \geq 70 years.
- 4.3 ECOG performance status \leq 2.
- 4.4 Sign a written informed consent form.
- 4.5 Adequate liver function (total bilirubin \leq 2mg/dL, SGPT or SGOT \leq x 4 ULN) and renal function creatinine clearance of \geq 50 mL/min (estimated by the Cockroft-Gault [C-G] formula).
- 4.6 Male patients must use an effective contraceptive method during the study and for a minimum of 8 weeks after study treatment.
- 4.7 Baseline LVEF $>/=$ 40%.

Exclusion:

- 4.8 Patients with \geq NYHA grade 3 heart disease as assessed by history and/or physical examination.

- 4.9 Patients who received more than one full course of prior hypomethylating agents azacitidine or decitabine
- 4.10 Have any other severe concurrent disease, or have a history of serious organ dysfunction or disease involving the heart, kidney, liver, or other organ system that may place the patient at undue risk to undergo treatment.
- 4.11 Patients with a systemic fungal, bacterial, viral, or other infection not controlled (defined as exhibiting ongoing signs/symptoms related to the infection and without improvement, despite appropriate antibiotics or other treatment).
- 4.12 Pregnant or lactating patients.
- 4.13 Any significant concurrent disease, illness, or psychiatric disorder that would compromise patient safety or compliance, interfere with consent, study participation, follow up, or interpretation of study results.
- 4.14 Any concurrent malignancy (with the exception of exclusion # 4.15)
- 4.15 Exceptions to # 4.14: a) Patients with treated non-melanoma skin cancer, in situ carcinoma, or cervical intraepithelial neoplasia, regardless of the disease-free duration, are eligible for this study if definitive treatment for the condition has been completed; b) Patients with organ-confined prostate cancer with no evidence of recurrent or progressive disease based on prostate-specific antigen (PSA) values are also eligible for this study if hormonal therapy has been initiated or a radical prostatectomy has been performed.

5.0 Treatment Plan

5.1 Schedule

Patients are randomized between 2 treatment arms:

Induction:

- A) SGI-110 60mg/m² subcutaneously (SQ) daily x 5
- B) SGI-110 60 mg/m² SQ daily x 5 + idarubicin 6mg/m² IV daily x 2

Cycles will be repeated every 4 to 6 weeks or longer as indicated by leukemia recurrence or recovery of normal hematopoiesis. Since efficacy from epigenetic treatment with agents such as SGI-110 may take longer to manifest, it is recommended that patients receive at least 2 courses of the above regimens regardless of their response.

If a patient does not achieve a CR or CR_i after a maximum of 3 induction courses, the patient will be taken off study unless the patient is deriving clinical benefit at which time continuation of protocol therapy will be allowed with prior PI approval.

Maintenance:

Patients who achieve a CR or CR_p during induction may receive up to 24 months of maintenance therapy every 4 to 8 weeks. The maintenance arm will be the same as the induction arm e.g. patients who are induced on SGI-110 + idarubicin are also maintained with SGI-110 + idarubicin.

- A) SGI-110 60mg/m² SQ daily x 5**
- B) SGI-110 60mg/m² SQ daily x 5 + idarubicin 6 mg/m² IV on Day 1**

- Patient may receive follow up laboratory tests from their local physician.
- All protocol-specific treatment decisions will be made by MD Anderson physician.
- The PI/treating physician must review all outside lab results, determine the clinical significance and sign/date the report.

5.2 Dose Modifications

Induction:

If a second induction course is considered, doses of each drug should be reduced by 25% for grade 3 drug-related non-hematological toxicities. Doses should be reduced by 50% for grade 4 drug-related non-hematological toxicities and/or life-threatening infections.

Maintenance:

Prior to each maintenance cycle, the ANC should be $\geq 1.0 \times 10^9/L$ and the platelet count $\geq 60 \times 10^9/L$, except for patients who are considered to have achieved a CRp following induction and in whom a platelet count of $< 60 \times 10^9/L$ will be allowed to continue. In addition, any nonhematological toxicity experienced by the patient must return to \leq grade 2 or baseline before the patient continues treatment with the study drugs. Doses missed or held during a cycle of treatment will not be made up and are recorded as being omitted. If a patient experiences multiple toxicities, dose adjustments will be based on the most severe toxicity.

Doses of SGI-110 and idarubicin may be reduced according to the following criteria: grade 3-4 (severe) drug-related nonhematologic toxicities (including life-threatening infections), or prolonged myelosuppression (hypocellular marrow [$<10\%$] and failure to recover the absolute neutrophil count [ANC] $\geq 1,000$ and platelet count $\geq 60,000$ by day 42): reduce both drugs by 25-33% as per Table below.

Dose level	SGI-110	Idarubicin
Start-0	60mg/m ²	6mg/m ²
-1 level	45mg/m ²	4mg/m ²
-2 level	30mg/m ²	3mg/m ²

Once doses have been reduced for drug-related non-hematologic toxicities, they should not be increased later on unless it is decided that the toxicity has completely resolved, was not drug-related, or that the benefit outweighs the risk.

Dose reductions are not necessary for alopecia, drug-related fever, fatigue, electrolyte abnormalities, or nausea/vomiting that can be controlled with supportive care measures. Left Ventricular Ejection Fraction should be done to monitor for congestive heart failure in patients receiving idarubicin following induction. .

All other dose modifications outside the above mentioned suggestions and which are considered to be in the best interest of the individual patient should be discussed with the Principal Investigator.

In general, in the combination arms, if those reductions are necessitated as described above, the doses of idarubicin may be reduced without reducing the SGI-110 doses.

Dose reductions other than the above may be considered if judged to be in the best interest of the patient. These include reductions in the number of days of SGI-110 or idarubicin if judged indicated, such modifications must however be discussed with and approved by the primary investigator.

All drug dose modifications will be clearly documented in the medical record to verify compliance with the protocol.

5.3 Concomitant Therapy

Necessary supportive measures for optimal medical care will be given throughout the study as determined by the treating physician and the patient's medical need. No concomitant chemotherapy (with the exception of prophylactic intrathecal therapy), immunotherapy, or therapy with monoclonal antibodies will be allowed during this study. Investigational agents that are not used for treatment of the leukemia per se (e.g. anti-infective prophylaxis or therapy) will be allowed. No concomitant medications will be captured as part of the protocol data.

Use of a colony-stimulating factor (e.g., G-CSF, GM-CSF, or erythropoietin) is at the discretion of the treating physician and is permitted if judged in the patient's best medical interest.

Prophylactic antibiotics, antifungals, and antiviral agents (e.g., levofloxacin, itraconazole, valacyclovir, etc.) are recommended; however, the use of these or other drugs will be left to the treating physician's discretion.

6.0 Pretreatment evaluation

History and physical, CBC with differential and platelets, Chemistry profile (at least creatinine, SGOT or SGPT, total bilirubin) within 14 days of therapy start.

Bone marrow aspirate and/or biopsy within 30 days of therapy start. The bone marrow evaluation will include cytogenetic studies, if not done in previous 3 months.

Pregnancy (urine or blood) test for women of childbearing potential within two weeks of start of therapy. Child bearing potential is defined as not post-menopausal for 12 months or no previous surgical sterilization.

Baseline LVEF.

7.0 Evaluation during Study

On Day 1 (+/- 7 days) of every cycle, the following tests and procedures will be performed:

- You will have a physical exam, including measurement of your weight
- Vital signs.
- Your performance status will be recorded.

CBC with differential and platelet counts at least once a week until remission, then every 2 to 4 weeks during therapy, and every 4 to 8 weeks thereafter as long as on study. No differential is needed if the WBC is $< 1.0 \times 10^9/L$.

Chemistry profile (at least creatinine, SGOT or SGPT, total bilirubin) at least weekly until remission, then every 4 to 8 weeks during therapy.

Bone marrow aspirate and/or biopsy starting on day 28 (± 7 days) of therapy and then every 2 weeks (± 7 days) as required by leukemia evolution until remission or non-response. Bone marrow tests can be ordered more frequently if mandated by development of peripheral blood counts. No repeat bone marrow is necessary if non-response or progressive disease can be unequivocally diagnosed from peripheral blood tests, or, in patients with a WBC ≤ 0.3 if the bone marrow test is considered non-contributory by the investigator at any time point (± 2 days).

LVEF every 3-4 cycles as indicated.

Optional. Blood 10cc pre-treatment, on Days 1 and 15 (+/- 2 days) of the first course to evaluate epigenetic modulation. (This will cover both the 5-day and 10-day regimens)

Follow-up Visits

After your last dose of study drug (after completion of all therapies), you will have follow-up visits. You will only have these visits if the disease has responded to the study drug. This can be done at home through your local cancer doctor as indicated (usually visit + routine CBC and chemistries every 2-3 months). Approximately every 6 months, you will return to Houston for a physical exam and blood (about 1 tablespoon) will be drawn for routine tests:

Chemistry profile (at least creatinine, SGOT or SGPT, total bilirubin).

8.0 Criteria for Response

8.1 Complete Remission (CR):

. Neutrophil count $\geq 1.0 \times 10^9/L$ and platelet count $\geq 100 \times 10^9/L$, and normal bone marrow differential ($\leq 5\%$ blasts)

8.2 Complete Remission without blood count recovery (CRI): Peripheral blood and bone marrow results as for CR, but with platelet counts of $< 100 \times 10^9/L$ or ANC $< 1.0 \times 10^9/L$

8.3 Partial Remission (PR):

Blood count recovery as for CR, but with both a decrease in marrow blasts of at least 50% and not more than 6 to 25% abnormal cells in the marrow.

8.4 Early mortality: Death within 14 days of first dose.

8.5 Patients who achieve a CR or CR_p during induction may receive up to 24 months of maintenance therapy every 4 to 8 weeks

8.6 Prior to each maintenance cycle, the ANC should be $\geq 1.0 \times 10^9/L$ and the platelet count $\geq 60 \times 10^9/L$, except for patients who are considered to have achieved a CRp following induction and in whom a platelet count of $< 60 \times 10^9/L$ will be allowed to continue.

9.0 Criteria for Discontinuation of Therapy

Patients can be discontinued from the study under the following conditions:

- 9.1 Patient's physician considers a change of therapy would be in the best interest of the patient.
- 9.2 Patient requests discontinuation or withdraws consent.
- 9.3 There is unacceptable toxicity (e.g., grade 4 nonhematologic toxicity), not controlled with dose adjustments.
- 9.4 There is a need for any treatment not allowed by the protocol.
- 9.5 Investigator determines that the patient has progressive disease after sufficient induction therapy.

Every 6 months, you will return to Houston for a physical exam and blood (about 1 tablespoon) will be drawn for routine tests.

10.0 Statistical Considerations

10.1.1 Update of the General Description/Sample Size February 01, 2017

This is a Phase II with 2 parallel arms study of SGI-110 in patients with newly diagnosed AML ≥ 70 years of age. The primary objective is to obtain an initial assessment of efficacy for the two SGI-110 regimens in this patient group:

- 1) SGI-110 single-agent for 5 days.
- 2) SGI-110 for 5 days combination with idarubicin for 2 days.

For each arm, we will enroll 20 patients. When all the arms have 20 patients then to be able to enroll more patients after the first 20 patients they have to satisfy the following rules: 1) there is more than 95% chance that the grade 3-4 non-hematological toxicity rate doesn't exceed 30%. 2) there is less than 10% chance that the 8-week mortality exceeds 15% and 3) there is more than 2.5% chance that the CR rate (CR+CRi) is more than 30%.

The arm or arms with the satisfying monitor rules above will continue to enroll an additional 20 patients. This will be decided through an interim analysis discussion with the Leukemia experts and the modality experts coordinating the study.

Complete Remission monitoring

The primary endpoint is the complete remission rate (CRR) evaluated after at least 2 cycles but would also be evaluated after 4 and 6 cycles if the patient is stable or improving. We have a target CRR of 30%, while a CRR of 15% is considered unacceptable. We will monitor complete remission using the Bayesian approach of Thall et al. [19]. The probability of complete remission

is denoted by P_{CR} . We assume $P_{CR} \sim \text{beta}(0.6, 1.4)$. Our stopping rule is given by the following probability statement: $\Pr(P_{CR} > 0.30 | \text{data}) < 0.025$. That is, we will stop the study if, at any time during the study, we determine that there is less than 2.5% chance that the CRR is more than 30%. This stopping rule will be applied in each arm. The stopping boundaries for complete remission, based on these assumptions and monitoring conditions are found in **Table 1**. We will apply these stopping boundaries starting from the first patient and in cohorts of 10. For example, accrual will cease if only 2 patients experiences complete remission among in the first 20 patients treated. The operating characteristics are summarized in **Table 2**. Both the decision rule and operating characteristics were calculated using the stopbound procedure in Stata version12.1.

Table 1. Stopping boundaries for Complete Remission (separately for each arm)

The number of patients evaluated for complete remission	10	20	30	40
The number of patients with complete remission	0	</=2	</=4	</=6

Table 2. Operating characteristics for Complete Remission (separately for each arm)

True Complete Remission Rate	Early Stopping Probability	Sample Size		
		25 th percentile	Median	75 th percentile
0.15	0.5994	20	30	40
0.20	0.3303	30	40	40
0.25	0.1528	40	40	40
0.30	0.0670	40	40	40
0.35	0.0255	40	40	40
0.40	0.0087	40	40	40

Toxicity Monitoring

We will monitor toxicity using the Bayesian approach of Thall et al. [19]. **A toxicity is defined as grade 3 or higher non-hematological toxicity occurring during the first two cycles.** Following are the rules for the monitoring of toxicities. The probability of toxicities is denoted by P_T . We assume $P_T \sim \text{beta}(0.6, 1.4)$. Our stopping rule is given by the following probability statement: $\Pr(P_T > 0.30 | \text{data}) > 0.95$. That is, we will stop the study if, at any time during the study, we determine that there is more than 95% chance that the toxicity is more than 30%. This stopping rule will be applied in each arm. The stopping boundaries for toxicities, based on these assumptions and monitoring conditions is found in **Table 3**. We will apply these stopping boundaries starting from the first patient and in cohorts of 5. For example, accrual will cease if 4 patients experiences toxicities among in the first 5 patients treated. The operating characteristics are summarized in **Table 4**. Both the decision rule and operating characteristics were calculated using the stopbound procedure in Stata version12.1.

Table 3. Stopping boundaries for Toxicities (separately for each arm)

The number of patients evaluated for toxicities	5	10	15	20	25	30	35	40
The number of patients with toxicities	4	6	8	10	12	14	16	18

Table 4. Operating characteristics for Toxicity Monitoring (separately for each arm)

True Toxicity Rate	Early	Sample Size
--------------------	-------	-------------

Stopping Probability		25 th percentile	Median	75 th percentile
0.10	0.0005	40	40	40
0.20	0.0149	40	40	40
0.30	0.1247	40	40	40
0.40	0.4581	15	40	40
0.50	0.8272	10	15	40

Mortality Monitoring

We will monitor 8-week mortality using the Bayesian approach of Thall et al. [19]. Following are the rules for the monitoring of 8-week mortality. The probability of 8-week mortality is denoted by P_M . We assume $P_M \sim \text{beta}(0.3, 1.7)$. Our stopping rule is given by the following probability statement: $\Pr(P_M > 0.15 | \text{data}) > 0.90$. That is, we will stop the study if, at any time during the study, we determine that there is more than 90% chance that the 8-week mortality is more than 15%. This stopping rule will be applied in each arm. The stopping boundaries for 8-week mortality, based on these assumptions and monitoring conditions is found in **Table 5**. We will apply these stopping boundaries starting from the first patient and in cohorts of 5. For example, accrual will cease if 3 patients died during the first 8 weeks among in the first 5 patients treated. The operating characteristics are summarized in **Table 6**. Both the decision rule and operating characteristics were calculated using the stopbound procedure in Stata version12.1.

Table 5. Stopping boundaries for Mortality (separately for each arm)

The number of patients evaluated for mortality	5	10	15	20	25	30	35	40
The number of patients died during the first 8 weeks	3	4	5	6	7	8	9	10

Table 6. Operating characteristics for Mortality Monitoring (separately for each arm)

True Mortality Rate	Early Stopping Probability	Sample Size		
		25 th percentile	Median	75 th percentile
0.05	0.0029	40	40	40
0.10	0.0298	40	40	40
0.15	0.1552	40	40	40
0.20	0.3790	20	40	40
0.25	0.6341	10	25	40

Statistical Analysis Plan

All patients who received at least 1 dose of the agent will be included in the intent-to-treat analysis for efficacy and safety. Demographic/clinical characteristics and safety data of the patients will be summarized using descriptive statistics such as mean, standard deviation, median and range (i.e. remission duration). Complete remission rates (CRR) will be presented with 95% confidence intervals. The association between CRR and patient and clinical characteristics will be

examined by Wilcoxon's rank sum test or Fisher's exact test. Survival time will be estimated using the Kaplan-Meier method. Patients who drop out of the study will be included in the time to event data as "censored data". The two-sided log-rank test will be used to assess the differences of time to events between groups.

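### The toxicity and mortality conditions for enrolling beyond 20 patients per arm do not match the stopping rules, and the operating characteristics in Tables 2, 4 and 6 omit them

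*Combined protocol and SAP*

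**What the plan says.** Section 10.1.1 enrols 20 patients per arm. For any arm to go further, "they have to satisfy the following rules":

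1. Toxicity: "there is more than 95% chance that the grade 3-4 non-hematological toxicity rate" is no higher than 30%.
2. Mortality: "there is less than 10% chance that the 8-week mortality exceeds 15"%.
3. Response: "there is more than 2.5% chance that the CR rate (CR+CRi) is more than 30"%.

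The consequence is that "The arm or arms with the satisfying monitor rules above will continue to enroll an additional 20 patients", for a maximum of 40. On who decides: "This will be decided through an interim analysis discussion with the Leukemia experts" and others coordinating the study.

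The same section then gives the stopping rules for each arm. Under Toxicity Monitoring, an arm stops if "we determine that there is more than 95% chance that the toxicity is more than 30"%. Under Mortality Monitoring, it stops if the posterior probability that 8-week mortality is above 15% is greater than 90%. Under Complete Remission monitoring, it stops if the posterior probability that the CR rate is above 30% is below 2.5%. Tables 1, 3 and 5 print the boundaries. Tables 2, 4 and 6 print early-stopping probabilities and sample-size percentiles, one endpoint at a time.

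For the stopping rule, the toxicity event is specified: "A toxicity is defined as grade 3 or higher non-hematological toxicity occurring during the first two cycles".

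**The concern.** If the expansion conditions simply restated the monitoring rules, each would be the complement of its stopping rule. Only the response condition is. For toxicity, not stopping means Pr(P_T > 0.30) ≤ 0.95, whereas expanding requires Pr(P_T > 0.30) < 0.05. For mortality, not stopping means Pr(P_M > 0.15) ≤ 0.90, whereas expanding requires it to be < 0.10. The expansion text nevertheless calls its conditions the monitor rules.

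For the same data at 20 patients, the two parts of Section 10.1.1 can therefore lead to different decisions about enrolling 20 more patients in an arm. If the expansion conditions are binding, the printed stopping probabilities and the many sample-size percentiles of 40 are not those of this trial. If they are not binding, the written expansion rule is wrong.

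The toxicity event differs as well. The expansion condition counts grades 3–4 with no time window. The stopping rule counts grade 3 and above in the first two cycles. With cycles every 4 to 6 weeks or longer (Section 5.1), two cycles last at least 8 to 12 weeks. A fatal toxicity after week 8 but within two cycles would count towards stopping but towards neither safety condition for expansion.

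**Working it through.** **Inputs (all Section 10.1.1).** Priors: beta(0.6, 1.4) for CR and for toxicity, beta(0.3, 1.7) for 8-week mortality. Looks: every 10 patients for CR, every 5 for toxicity and mortality. Maximum 40 per arm.

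**Step 1: boundaries.** With x events in n patients, the posterior is beta(a + x, b + n − x). Applying the stopping rules at each look reproduces Tables 1, 3 and 5 exactly.

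**Step 2: cut-offs at n = 20.**

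| Endpoint | Expansion condition | Stopping rule |
|---|---|---|
| Toxicity | Pr(P ≤ 0.30) = 0.985 at x = 2, 0.944 at x = 3: needs ≤ 2 | Pr(P > 0.30) = 0.906 at x = 9, 0.961 at x = 10: stops at ≥ 10 |
| Mortality | Pr(P > 0.15) = 0.058 at x = 1, 0.212 at x = 2: needs ≤ 1 | 0.845 at x = 5, 0.939 at x = 6: stops at ≥ 6 |
| CR/CRi | Pr(P > 0.30) = 0.015 at x = 2, 0.056 at x = 3: needs ≥ 3 | stops at ≤ 2 |

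Only CR matches. An arm with 3 toxicities (15% observed, half the threshold) or 2 deaths (10% observed, under the threshold) fails to expand.

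**Step 3: early stopping, one endpoint at a time.** This is an exact binomial recursion over the looks, counting stops before 40. The last column ends the arm at 20 if its expansion condition fails.

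| True rate | Table 4 or 6 | Stopping rule only | With expansion condition |
|---|---|---|---|
| Toxicity 0.10 | 0.0005 | 0.0006 | 0.323 |
| Toxicity 0.20 | 0.0149 | 0.0149 | 0.794 |
| Toxicity 0.30 | 0.1247 | 0.1231 | 0.9645 |
| Mortality 0.05 | 0.0029 | 0.0024 | 0.264 |
| Mortality 0.10 | 0.0298 | 0.0334 | 0.608 |
| Mortality 0.15 | 0.1552 | 0.1527 | 0.8245 |

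The printed values match the stopping rules alone, so the tables contain no expansion condition. With it, the sample-size quartiles change from 40/40/40 to 20/20/20 at toxicity 0.20, and from 40/40/40 to 20/20/40 at mortality 0.10.

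**Step 4: meeting both safety conditions.** The binomial probabilities of ≤ 2/20 toxicities are 0.9245, 0.677 and 0.206 at true rates 5%, 10% and 20%. Those of ≤ 1/20 deaths are 0.736 and 0.392 at 5% and 10%. Under independence the joint probability is the product. Under any dependence it lies between max(0, a + b − 1) and min(a, b).

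| Toxicity / mortality | Independent | Range |
|---|---|---|
| 20% / 10% | 0.206 × 0.392 = 0.081 | 0 to 0.206 |
| 10% / 5% | 0.677 × 0.736 = 0.498 | 0.413 to 0.677 |
| 5% / 5% | 0.9245 × 0.736 = 0.680 | 0.660 to 0.736 |

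**Step 5: all three criteria, true CR rate 30%.** The CR rule alone stops an arm before 40 with probability 0.066 (Table 2: 0.0670). Under independence at 20%/10%:

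- stopping rules only: 1 − 0.934 × 0.9851 × 0.9666 = 0.11
- with the expansion conditions: 1 − 0.934 × 0.206 × 0.392 = 0.92

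The corresponding pairs are 0.07 and 0.53 at 10%/5%, and 0.07 and 0.36 at 5%/5%. If instead every 8-week death also counts as a toxicity and cannot be a CR, simulation gives 0.10 and 0.84, 0.07 and 0.43, and 0.07 and 0.31.

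**Side finding.** Table 4 at toxicity 0.50 prints early stopping of 0.8272 and a 75th percentile of 40. If 82.7% of arms stop before 40, that percentile must be below 40. The exact cumulative stopping is 0.738 by n = 25 and 0.793 by n = 30, so it is 30.

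**The case against.** A lenient boundary applied throughout and a stricter one-time test before expansion can coexist. Read literally, an arm with 3 to 9 toxicities or 2 to 5 deaths has a defined outcome: it completes 20 and does not expand. Each table is titled for one endpoint and claims nothing about the whole trial, and Table 2 is correct for the CR rule. Ending at 20 is also not a safety stop, so setting 0.0149 beside 0.794 compares different events. Finally, the interim discussion may not apply the conditions mechanically, and the short toxicity wording in the expansion rule may be only a summary of the full definition.

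Much of this is fair. A stricter expansion test is a legitimate design, and the figures in the last column of Step 3 are probabilities of ending before 40 for any reason. But if that test is intended, no cut-off or operating characteristic is given for it, and the sample-size percentiles in all three tables, including Table 2, assume that no arm is held at 20 for safety. If it is loose wording, the rule needs correcting. Leaving the decision to a discussion does not help when that discussion is given two different standards.

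Independence of the outcomes is indeed implausible, since a fatal toxicity can count for both safety endpoints. The joint figures are therefore shown under an alternative too; they fall somewhat and lead to the same conclusion.

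**Conclusion.** The concern holds, with high confidence, and should be fixed before any arm reaches the expansion decision. The cut-offs at 20 patients follow from the stated priors and thresholds with no further assumption: at most 2 toxicities and at most 1 death to expand, against 10 and 6 to stop. The documents do not settle which rule is meant.

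The consequence is large wherever the expansion conditions apply. Even at the mildest rows of Tables 4 and 6, they hold back 32% of arms (toxicity 10%) and 26% (mortality 5%).

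The true rates used here are assumptions, because the plan gives no expected toxicity or mortality rate apart from prior means equal to the thresholds (30% and 15%). At those means an arm would pass the toxicity condition with probability 0.036 and the mortality condition with probability 0.176. All figures assume that the interim discussion applies the rules as written.

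**What to change.** In Section 10.1.1 the sponsor should:

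- State which rule governs enrolment beyond 20, and reconcile the expansion paragraph with Toxicity Monitoring and Mortality Monitoring.
- Print the integer cut-offs at n = 20 for that rule.
- Say how far the interim discussion may depart from it.
- Use one toxicity definition, with the same grades and time window, in both places.
- Recompute the operating characteristics for the rule actually used, with all three criteria acting together, and correct the Table 4 row for 0.50 in the same rerun.

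The cost is a short text amendment and a rerun, with no extra patients. If the stricter conditions are kept, the stated sample-size figures become less favourable. If the stopping rules govern, the protocol gives up the stricter safety test before expansion. That choice is the sponsor's.

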2.4 Update of January 27, 2017

As of February 2017, 34 patients have been treated on study. The complete response in the 4 treatment arms are as follows: 4 out of 8 patients responded in the SGI-110 for 5 days arm; 5 out of 9 patients responded in the SGI-110 for 10 days arm; 7 out of 8 patients responded in the SGI+idarubicin arm and 3 out of 9 patients responded in the SGI+cladribine.

In addition, Astex, the sponsoring company, conducted a separate multi-institutional study of SGI-110 60mg/m² for 5 and 10 days in older patients with newly diagnosed AML who were not candidates for intensive chemotherapy (8). A total of 103 patients were treated, 51 patients were treated on the 5-day and 52 patients were treated on the 10-day regimens. The characteristics of the 2 study groups were well-balanced. Overall the CR rates were 19/51 = 37% on the 5-day regimen and 16/52 = 31% on the 10-day regimen. The overall response rates were 57% and 48%, respectively. The median survival were 10.5 months on the 5-day regimen and 9.5 months on the 10-day regimen ($p=0.70$). Side-effects, including myelosuppression, were similar in the 2 study groups. The 60-days all-cause mortality was also similar between the two study groups.

The study concludes that both schedules (SGI-110 given in 5-day and SGI-110 given in 10-day) were similar (8).

Based on the above findings, and after discussion with the Biostatistical collaborators, [name] and [name], it was decided to close the 2 arms of SGI-110 for 10 days (based on the Astex study) and SGI-110 + cladribine (low CR rate), and continue the study, with the same Bayesian statistical design, only in the 2 arms of SGI-110 for 5 days and SGI-110 + idarubicin.

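### Does the 30% CR+CRi condition for expanding an arm, already certain to be met by both continuing arms in February 2017, need to be replaced?

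*Combined protocol and SAP*

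**What the plan says.** Section 10.1.1, dated 1 February 2017, plans 20 patients in each of two arms and 20 more in an arm that meets three rules on toxicity, 8-week mortality and response. The response rule is that "there is more than 2.5% chance that the CR rate (CR+CRi) is more than 30" per cent. On meeting all three, "The arm or arms with the satisfying monitor rules above will continue to enroll an additional 20 patients". The next sentence refers the decision to an interim discussion with the leukemia and modality experts.

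The Complete Remission monitoring paragraph adds: "We have a target CRR of 30%, while a CRR of 15% is considered unacceptable". An arm stops if the posterior probability of a rate above 30% is below 0.025, with a beta(0.6, 1.4) prior and looks every 10 patients. Table 1 gives the bounds 0/10, 2/20, 4/30 and 6/40. The operating characteristics are in "Table 2. Operating characteristics for Complete Remission (separately for each arm").

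Section 2.4 gives the counts known at the update: "4 out of 8 patients responded in the SGI-110 for 5 days arm", 5 of 9 on the 10-day schedule, and "7 out of 8 patients responded in the SGI+idarubicin arm and 3 out of 9 patients responded in the SGI+cladribine" arm. After discussion with the biostatistical collaborators, the 10-day arm was closed on outside data. The other decision reads: "SGI-110 + cladribine (low CR rate), and continue the study, with the same Bayesian statistical design", in the two remaining arms. For the outside study it reports: "Overall the CR rates were 19/51 = 37% on the 5-day regimen and 16/52 = 31% on the 10-day regimen".

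**The concern.** The response rule is presented as a live condition for expansion, yet the counts in section 2.4 appear to have settled it already. Three responders in 20 satisfy it, and the continuing arms had 4 and 7 after 8 patients each. A reader of Table 2 would expect an arm with a true rate of 15% to stop early about 60% of the time, which is no longer so from the counts in hand.

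The cladribine arm sharpens the point. It was closed for a low rate at 3/9 = 33%, which is above the 30% target, so the written threshold does not look like the standard that was applied. The outside data for the 5-day regimen (19/51 = 37% CR alone) also exceed the target. At stake would be an expansion decision with no working efficacy check, and a report that an arm met its response rule when it could not have failed.

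**Working it through.** **Inputs.** Prior beta(0.6, 1.4), threshold 0.30, cut-off 0.025 and looks at 10, 20, 30 and 40 (section 10.1.1). Counts of 4/8, 7/8 and 3/9 (section 2.4). Section 2.4 does not say whether these are CR or CR+CRi. If they are CR alone, CR+CRi is at least as large and the argument is unaffected.

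**Reproducing the plan.** After x responders in n patients the posterior is beta(0.6 + x, 1.4 + n − x). The bound is the largest x with Pr(P > 0.30) < 0.025.

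| n | at the bound | one responder more |
|---|---|---|
| 10 | 0: 0.0065 | 1: 0.0633 |
| 20 | 2: 0.0153 | 3: 0.0564 |
| 30 | 4: 0.0152 | 5: 0.0437 |
| 40 | 6: 0.0130 | 7: 0.0330 |

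This is Table 1 exactly. An exact binomial recursion from zero patients, with looks at 10, 20 and 30, gives early-stopping probabilities of 0.593, 0.332, 0.157, 0.066, 0.026 and 0.009 at true rates of 0.15 to 0.40 in steps of 0.05. Table 2 prints 0.5994, 0.3303, 0.1528, 0.0670, 0.0255 and 0.0087. The tables are sound as operating characteristics from the first patient.

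**From the counts in hand, if the 8 patients per arm count.** Suppose no further patient responded before 20. The 5-day arm would be at 4/20 (Pr = 0.146) and the idarubicin arm at 7/20 (0.658), both above 0.025. Before 40, the 5-day arm can stop only at 4/30, which needs 0 responses in the next 30 − 8 = 22 patients. At a true 15% that is 0.85^22 = 0.028; at 30% it is 0.0004. The idarubicin arm cannot reach any bound, since 7/40 gives 0.033.

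**How likely is the scenario that makes this look alarming?** At a true 15%, P(X ≥ 4 of 8) = 0.021 and P(X ≥ 7 of 8) = 0.00001. The contrast between 0.59 and 0.028 or 0 therefore conditions on a rate that the data already make implausible.

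**The 33% scenario.** A rate of 33% is above the 30% target, so the design intends such an arm to continue. Even from zero patients it stops before 40 with probability only 0.035. The early counts change almost nothing here.

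**The cladribine arm.** At 3/9, Pr(P > 0.30) = 0.546, so no bound in Table 1 was near. The floor says when an arm must stop; it does not say that an arm above it must continue. The other arms stood at 50%, 56% and 88%, against which 33% is low.

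**Would a higher target help?** With the same prior and cut-off, targets of 0.40, 0.45 and 0.50 (assumed for illustration; the documents give none) put the bound at 20 patients at 4, 4 and 5. The idarubicin arm already has 7, so it still cannot fail at 20. At a target of 0.40 its bound at 30 is 7, so it stops before 40 only with 0 responses in the next 22 patients (0.028 at a true 15%), the same remote event as in the 5-day arm now.

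**The case for a change.** The strongest case for a change is that the rule was restated when its result could already be worked out. A condition that cannot fail is not a test, and from-zero operating characteristics printed beside it can mislead. Closing an arm at 33% without stating a criterion adds to the impression that an unwritten standard was in use.

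Part of this stands. If the earlier patients count, the response rule adds nothing to the decision at 20. Section 10.1.1 does not say whether they count, and section 2.4 does not say what low was measured against. These are missing details, and a reader can fill them: the wording about continuing with the same design points to counting from the first patient, and the counts by arm are printed.

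The rest does not stand. Any futility floor becomes slack once an arm does well, and operating-characteristic tables are not normally rewritten to condition on interim data. Nor is the expansion decision left without a check. The toxicity and mortality rules remain, and the plan sends the decision to an expert discussion that may look beyond the floor. The outside 37% has a 95% interval of 24% to 52%, which includes 30%, so it does not show the target to be too low. A new target chosen with the results by arm known would carry its own hazard and would need a source that the documents do not supply.

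**Conclusion.** The arithmetic behind the concern is right and the conclusion does not follow. If the 8 patients per arm count toward the first 20, both continuing arms are certain to meet the response rule, and the decision at 20 rests on toxicity, 8-week mortality and the expert discussion. This is a floor doing what it was built to do. Tables 1 and 2 are correct for what they describe, and closing the cladribine arm above the floor contradicts no stated rule.

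Raising the target would be a debatable trade-off made after seeing the data, and it would leave the idarubicin arm equally unable to fail at 20. Stating that the rule is assured, and how 3/9 was judged low, would help a reader but alter no result.

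The conclusion assumes that the earlier patients count. If counting restarted, the concern largely disappears: Table 2 would apply in full, and an arm at a true 15% would fail at or before 20 patients with probability 0.40 (the look at 20 alone) to 0.44 (with the look at 10). Under either reading the plan can stand.
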